## 8.2.9 Pregnancy

As per inclusion criteria, women of childbearing potential must have a negative serum pregnancy test at SCR and a negative urine pregnancy test within 24 hours prior to each vaccination. In addition, they must have used an acceptable method of contraception for 30 days prior to the first vaccination, must agree to use an acceptable method of contraception during the trial, and must avoid becoming pregnant for at least 28 days after the last vaccination. Nevertheless, IMP exposed pregnancies cannot be excluded with certainty. Subjects who become pregnant prior to the first vaccination will be excluded from the trial and are regarded as screening failure. Subjects who become pregnant during the active trial period (up to and including one month [minimum 28 days] after receiving a dose of vaccine) must not receive additional doses of vaccine but may continue other trial procedures at the discretion of the investigator (see [Section 4.2.5](#)). All reports, where the embryo or foetus may have been exposed to the IMP (either through maternal exposure or transmission of a medicinal product via semen following paternal exposure), should be followed-up until delivery in order to collect information on the outcome of the pregnancy.

Subjects should be instructed to notify the investigator if it is determined – also after completion of the trial – that they became pregnant either during the trial or within one month (minimum 28 days) after receiving the last vaccine dose.

## 8.3 Reporting

### 8.3.1 Reporting of SAEs

All SAEs occurring throughout the entire course of the trial have to be reported to the CRO Drug Safety (DS) Department. The CTS has to send the completed SAE form by e-mail or fax to the CRO DS Department within 24 hours of becoming aware of the SAE.

If not reported via an eCRF, SAE reports should be faxed to the following number:

(b) (1) (A)

[figure not shown]
The investigator should not delay reporting because of missing information. Nonetheless, the report should be as complete as possible. This initial notification should include, as a minimum, sufficient information to permit identification of the following:

- the reporter (investigator's name and contact information)

- the subject
- involved trial medication
- AE(s)
- seriousness criterion and/or criterion for AESI
- date of onset

The CRO DS Department alerts BN DS Department of all SAEs and provides the available information within 24 hours to BN DS. BN is responsible for expedited as well as periodic reporting to the involved regulatory authorities (e.g. FDA, EMA, Paul Ehrlich Institut [PEI]) according to applicable laws and guidelines. Regulatory authorities will be notified as soon as possible but no later than seven days after first knowledge of fatal or life-threatening unexpected SAE with an at least possible relationship to the IMP (SADR) and no later than 15 days after knowledge of any other unexpected SADR. In addition BN will report the SAEs to the DSMB, while the investigator or the CRO is responsible for reporting to the Ethics Committees or Institutional Review Boards. [Figure 2](#) outlines the reporting process and timelines for SAEs.

**Figure 2 Algorithm for Reporting of SAEs**

### **8.3.2 Reporting of AESIs**

AESIs occurring throughout the entire course of the trial will be reported in the AE section of the eCRF by marking the appropriate tick box. AESIs have to be reported in the eCRF immediately after detection. An automatic email notification will be sent to the relevant project members as soon as an AESI was reported. A periodic report of AESIs will be provided from the CRO to BN Drug Safety.

[figure not shown]
[Figure 3](#) outlines the reporting process and timelines for AESIs.

### **8.3.3 Reporting of Pregnancy**

If a subject becomes pregnant during the active trial period (up to and including one month [minimum 28 days] after receiving a dose of vaccine) this must be reported to BN on a Pregnancy Report Form within 24 hours of the investigator's becoming aware of the event.

A pregnancy should be followed to term, any premature terminations reported, and the health status of the mother and child including date of delivery and the child's gender and weight should be reported to BN as soon as possible after delivery.

Any event during pregnancy fulfilling the criteria for an SAE will be reported as SAE to BN/CRO DS (see [Section 8.3.1](#)). However, hospitalization for delivery is a prospectively planned hospitalization and is not considered a SAE per se.

**Figure 3 Algorithm for Reporting of AESIs**

## 9 Statistical Considerations

The primary endpoint of this trial is to compare the occurrence, relationship and intensity of any serious and / or unexpected Adverse Event at any time during the trial. This analysis will be descriptive.

### 9.1 Randomization Procedure

Randomized treatment assignments for the subjects will be done after confirmation of subject's eligibility. Subjects will be allocated randomly across the trial into Group 1, Group 2 or Group 3. Randomization will be stratified by CTS in a 1:1:1 ratio.

Please refer to trial protocol synopsis (see [Section 1.5](#)).

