### 4.2.1 Screening Phase

All subjects must be thoroughly informed of all aspects of the trial (e.g. trial visit schedule, required evaluations and procedures, risks and benefits) as described in the informed consent form (ICF). The ICF and the statement about the Health Insurance Portability and Accountability Act (HIPAA) must be reviewed with the subject and signed and dated by the subject and the Investigator, or person designated by the investigator, who conducted the informed consent discussion before proceeding with any evaluations or procedures required by this protocol.

After ICF has been collected, subjects will enter a screening period of up to 28 days before the first vaccination.

Screening Visit (Days -28 to -1)

The following tasks will be performed
 
 
• Subject to read, sign and date ICF and HIPAA
 
• Check inclusion/exclusion criteria
 
• Obtaining medical history
 
• Obtaining HIV specific medical history
 
• Check vaccination history (previous smallpox vaccination or vaccination with a pox-virus-based vaccine) and absence of smallpox vaccination scar
 
• Complete physical examination including auscultation of heart and lungs and measurement of body weight and height
 
• Evaluation of vital signs
 
• Cardiac assessment (Section 8.2.7) 
 
○ Calculation of the individual cardiac risk factor (after receipt of lab results for cholesterol)
 
○ Evaluation of family cardiac risk factors
 
○ Perform baseline ECG
 
 
 
• Recording of AEs/SAEs/AESIs
 
• Recording of prior and concomitant medication
 

- Counseling on avoidance of pregnancy: Review of acceptable contraceptive methods and recent menstrual history with WOCBP
- Blood draw (2 ml) for CD4 count
- Blood Draw (4 ml) for viral load
- Blood draw for safety laboratory (7 ml) including
  - Serum pregnancy test (WOCBP only)
  - Hematology & serum chemistry
  - Troponin I
  - Total cholesterol, High-density Lipoprotein (HDL) and Low-density Lipoprotein (LDL)

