## 7.1 Humoral Immunogenicity

Immunogenicity testing will be performed on samples obtained from subjects of all three groups on trial Visit 1, Visit 3, Visit 4, FU1 and FU 2. Further, immunogenicity testing will be performed on samples obtained from subjects of Group 3 on trial Visits 6 and 7. Blood samples obtained on vaccination visits (i.e., Visit 1, Visit 3 and Visit 6) will be drawn prior to vaccination.

Antibody responses to MVA-BN® smallpox vaccine will be measured using a vaccinia-specific ELISA and vaccinia-specific PRNT, both assays established and validated at BN. The immunogenicity analysis will be performed at BN. All personnel involved in immunogenicity testing will be blinded to subject randomization details.

The procedures for the analytical tests performed are outlined in [Sections 7.1.1](#) and [7.1.2](#) below. The SOPs, effective at the time of testing will be filed in the electronic Trial Master File.

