### Baseline

If not otherwise specified, 'Baseline' refers to the last measurement before the first injection of trial drug for a given parameter. This is either at Visit 1 or Screening Visit (SCR), or latest re-screening as appropriate. If there is missing vital sign data at Visit 1 then data obtained at the Screening Visit or latest re-screening visit will be used to impute the missing data. These data

will be summarized as Baseline data without specification of which visit was used. However, at all other visits no imputation will be used and the actual visit used will be specified in tables or listings.

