### **Geometric Mean Titer**

The Geometric Mean Titer (GMT) is calculated by taking the antilogarithm of the mean of the  $\log_{10}$  transformed titers. Antibody titers below the DL will be given an arbitrary value of “1” (one) for the purpose of this calculation.

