## 3 Statistical Methods

### 3.1 Planned Sample Size

In addition to the below sample size calculations for the immunogenicity endpoints, a sample size of 30 per treatment group also allows for the detection of AEs with an incidence of at least 1 in 10 with a probability of detection of at least 95%.

A sample size of 30 in each group will have 80% power to detect a difference in means of 0.74 x standard deviation (SD) using a two-group t-test with a 5% two-sided significance level. This means that a difference  $\Delta$  can be detected with  $\Delta / SD > 0.74$ . Taking into account the SD of 0.85 for the  $\log_{10}$  PRNT titers the detection of a  $\log_{10}$  PRNT difference of 0.629 can be detected (or a difference in titers on the original titer scale by a factor of 4). For the ELISA where the  $\log_{10}$  SD is at most 0.42 a difference of 0.311 can be detected, i.e. a difference in titers by a factor of 2 on the original scale can be detected.

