### 3.5.5 Demographic and Other Baseline Data

All listings will be based on the screened subjects with screen failures and subjects randomized but not treated considered as two separate trial groups. However tables of the descriptive statistics for the demographics will only be produced for the FAS and PPS.

Descriptive statistics will be presented for the continuous demographic variables, age, height, and body weight. Note that the value obtained on the date of the actual Screening Visit is used for age, height and body weight calculations (hence also for BMI) and not the date of any partial Re-screening Visit.

Age is calculated using the following formula:

AGE = Year of Screening Visit – Year of Birth;  
if Month of Screening Visit < Month of Birth then AGE → AGE – 1;  
if Month of Screening Visit = Month of Birth  
and Day of Screening Visit < Day of Birth then AGE → AGE – 1

Frequencies and percentages of subjects will be tabulated for the categorical variables sex, race and ethnicity in the same table by treatment group and overall. Percentages will be based on the total number of subjects in the relevant population.

Descriptive statistics for the demographic data will be produced by treatment group.

A summary of medical history by Preferred Term (PT) and System Organ Class (SOC) will be produced for each treatment group.

Non-treatment emergent AEs will be listed by body system and preferred term. Relative day of onset and duration of non-treatment emergent AEs will be calculated as described in [Section 3.3.3](#). Pre-treatment Adverse Events are defined as AEs with start date after the subject was screened for the trial but before the first injection was received. These events are to be reported.

Frequency summaries of the history of HIV infection, AIDS defining conditions, circumstances of HIV infection, and HIV related illness will be produced by treatment group.

Summary statistics of the historical viral load and CD4 statistics (year of diagnosis, lowest CD4 count previously documented, CD4 nadir, CD4 count at screening, highest viral load during up to six months ago, viral load at screening) will also be presented stratified by treatment group.

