### Geometric Mean Titers (GMTs)

GMTs measured by ELISA and PRNT will be calculated at Visits 1, 3, 4, 6, 7, FU 1 and FU 2 for each treatment group and for combined groups as indicated.

Descriptive statistics will be derived by visit including number of observations available at each visit (n) and GMT with 95% CI (derived by the antilogarithm of the 95% CI of the  $\log_{10}$  titer transformations). GMTs and upper and lower confidence limits will be displayed to one decimal place.

The ratio of the GMTs will be presented between Group 2 and the combined Group 1 / Group 3 at Visit 4 along with the 95% CI. Similarly, the ratio of the GMTs will be presented between

Group 3 at Visit 7 and Group 1 / Group 2 separately at Visit 4, and at the FU Visits (FU 1 and FU 2) the ratios of the GMTs will be presented between Group 3 and Group 1 / Group 2 separately. Lastly, the ratios of the GMTs at Visit 1, 3, 4, FU 1 and FU 2 will be presented between Group 1 and Group 2 / Group 3 separately.

A line chart will be presented showing the GMTs measured by ELISA and PRNT per treatment group for each visit for the PPS and the FAS.

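### The GMT ratios use neither the randomization stratum (site) nor screening CD4; prespecified adjustment is a cheap gain in precision if the two are prognostic enough

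*Protocol*

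**What the plan says.** Protocol 9.1 sets the allocation: "Randomization will be stratified by CTS in a 1:1:1 ratio". The synopsis allows up to 10 sites. Protocol 4.2.1 lists for every screened subject "Blood draw (2 ml) for CD4 count", and inclusion criterion 5 limits that count to 100–500 cells/µl.

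SAP 3.5.8 presents the ratio of GMTs for Group 2 against the "combined Group 1 / Group 3 at Visit 4 along with the 95% CI". Further ratios compare Group 3 at Visit 7 with Groups 1 and 2 at Visit 4, and the groups pairwise at other visits. A GMT is the antilog of a mean log10 titer, and "Antibody titers below the DL will be given an arbitrary value of" one. The SAP says how the CI of a GMT is obtained but not how the CI of a ratio is. It names no stratum or covariate.

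Baseline CD4 appears in SAP 3.5.5 only as "Summary statistics of the historical viral load and CD4 statistics" by group, and later counts are treated as laboratory data. SAP 3.6 lists no departures from the protocol.

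**The concern.** When randomization is stratified by site and site affects titers, an analysis that ignores site keeps an unbiased estimate but leaves between-site variation in the error term. The same holds for a baseline value that predicts the outcome. The CI is then wider than the data allow.

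The GMT ratios are how the trial addresses whether more doses improve the response, and with 30 subjects per group they will be imprecise. The SAP commits to being followed completely and to flagging other analyses as unplanned, so an adjustment added after database lock would carry that label.

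**Working it through.** **The plan's own figure.** With 30 v 30, a two-sided 5% t-test and a difference of 0.74 SD, noncentral-t power is 80.5%, against the stated 80%. For PRNT, 0.74 × 0.85 = 0.629 (10^0.629 = 4.26-fold). For ELISA the SAP says "SD is at most 0.42 a difference of 0.311 can be detected": 0.74 × 0.42 = 0.311 (2.05-fold). The plan's figures reproduce.

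**Unadjusted CI.** The SAP names no method for the ratio, so I take the pooled t interval that matches the sample-size section. Half-width = t × SD × √(1/n₁ + 1/n₂) on the log10 scale.
- PRNT, 30 v 30: 2.002 × 0.85 × √(2/30) = 0.439, so the CI is the ratio ×/÷ 2.75.
- ELISA, 30 v 30: 2.002 × 0.42 × √(2/30) = 0.217, so ×/÷ 1.65.
- PRNT, 30 v 60 (Group 2 v Groups 1 and 3): half-width 0.378, so ×/÷ 2.39.

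**Adjusted CI.** The SD is multiplied by √(1 − R²), where R² is the share of within-group log10-titer variance explained. There is a small penalty for up to 9 site terms, one CD4 term and chance imbalance. The documents give no R², so all prognostic inputs are assumed.

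Simulation (2,500 runs per cell; 2,000 for 25% loss): 10 sites, either 9 each or 27, 15, 12, 9, 9, 6, 3, 3, 3, 3; CD4 uniform on 100–500; 0 or 10% loss unless stated; 25% loss run on the uneven sites. Entries are CI width, adjusted ÷ unadjusted, over Group 2 v 1 and Group 2 v 1+3. Floored means set to 1.

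| Site ICC, CD4–titer r | No floor | 25% floored | 60% floored | 25% loss |
|---|---|---|---|---|
| none | 1.001–1.016 | – | – | 1.018–1.028 |
| 0.02, 0.1 | 0.988–1.003 | 0.989–1.003 | – | 1.005–1.015 |
| 0.05, 0.2 | 0.958–0.975 | 0.960–0.979 | 0.972–0.986 | 0.976–0.986 |
| 0.10, 0.4 | 0.866–0.883 | 0.876–0.890 | 0.909–0.924 | 0.886–0.894 |

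**Hand check.** Taking R² ≈ ICC + r² gives 0.03, 0.09 and 0.26. Then √(1 − R²) = 0.985, 0.954 and 0.860. With a penalty of about 1.01 these become 0.995, 0.964 and 0.869, in line with the no-floor column.

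**Harder cases (assumed), Group 2 v 1+3.**
- Very small sites (30, 20, 12, 8, 6, 5, 4, 2, 2, 1) with 25% loss: 1.021 at (0.02, 0.1) and 0.994 at (0.05, 0.2).
- Loss of 10% in Groups 1 and 2 and 35% in Group 3: 1.027 with no prognosis, 1.013 at (0.02, 0.1) and 0.981 at (0.05, 0.2).

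**Break-even.** If the width ratio with no prognosis is w, R² must exceed 1 − 1/w². For w = 1.001 this is 0.2%; for 1.016, 3.1%; for 1.028 (25% loss, Group 2 v 1+3), 5.4%.

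**On the titer scale, 30 v 30, no floor.** PRNT: 0.439 × 0.958 to 0.968 gives ×/÷ 2.64–2.66 at (0.05, 0.2), and 0.439 × 0.866 to 0.877 gives 2.40–2.43 at (0.10, 0.4). ELISA: 1.61–1.62 and 1.54–1.55.

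**Coverage.** At (0.10, 0.4) the unadjusted CI covers 95.8–96.7% and the adjusted CI 94.8–95.5%.

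**Unequal SDs.** If Group 2's SD is 1.25 times the others', the true variance factor for Group 2 v 1+3 is 1.5625/30 + 1/60 = 0.0688. The common-variance model estimates (1.5625 + 1 + 1)/3 × 0.05 = 0.0594, so its standard error is about 7% too small. Simulated coverage is 92.4% with covariates and 93.1% without. Welch intervals stay at 94.9–95.5%.

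**The case against.** The strongest reply is that this is a preference. The primary endpoint is descriptive safety; the GMT ratios are secondary and no test is planned; the unadjusted analysis is valid; and a gain of 1 to 4% would rarely change a reading. All of that stands, and it rules out calling this a defect.

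The documents also hint that prognosis may be weak. CD4 is confined to 100–500 cells/µl on stable antiretroviral therapy. All titers come from one organization: "The immunogenicity analysis will be performed at BN". Protocol 2.6.4 reports similar PRNT GMTs in HIV-infected and healthy subjects. On the other side, the same section notes a tendency to lower ELISA responses in HIV infection, and Protocol 2.7 treats CD4 as a measure of how suppressed the immune system is. Neither set of remarks gives a coefficient.

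Three technical objections also stand and shape the fix. An equal-weight mean of Groups 1 and 3 is not the SAP's combined group when their sizes differ. That is likely in the per protocol set, where Group 3 must also complete Visits 6 to 8. Very small sites need a full pooling rule. A common-variance CI can under-cover if group SDs differ.

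A reader might infer that adjustment must narrow the CIs whenever site or CD4 is prognostic at all. It need not: with weak prognosis and heavy loss or very small sites the CI can be about 2% wider.

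**Conclusion.** The point holds as an optional improvement in precision. The GMT ratios leave out the randomization stratum and a baseline value already collected on everyone. Whether that costs anything depends on prognostic strengths that the documents do not give. The outcomes studied are asymmetric: at worst about 3% wider if neither covariate matters, at best about 13% narrower if both matter strongly. Flooring many titers at 1 brings the best case down to about 8%.

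A reader might also infer that ignoring the stratum biases the ratios or makes their CIs invalid, or that the trial is underpowered as a result. The documents support neither. Randomization protects the unadjusted estimate, its CI errs on the conservative side if site is prognostic, the stated power reproduces, and no hypothesis test of the titers is planned.

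**What to change.** In SAP 3.5.8, before database lock, prespecify:

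- **Model.** Each post-vaccination GMT ratio and its 95% CI come from a linear model of log10 titer on group (all three), site and log10 screening CD4, with t-based limits back-transformed. Take CD4 under the SAP's Baseline rule, which "refers to the last measurement before the first injection of trial drug for a given parameter".
- **Sites.** Set the pooling once from counts at randomization. Pool sites with fewer than 3 subjects together; merge a lone small site with the next smallest. Use the same grouping for every visit and for both analysis sets.
- **Group 2 v combined Groups 1 and 3.** Weight Groups 1 and 3 by their numbers in the analysis set. The comparator then stays the SAP's combined group and matches the seroconversion comparison. The simulated Group 2 v 1+3 ratios used equal weights, which is the same thing when sizes are equal. With 27, 27 and 19.5 subjects in Groups 1, 2 and 3 (10%, 10% and 35% loss), and ignoring covariates, the variance factor is 1/27 + 1/46.5 = 0.0585, against 1/27 + (1/27 + 1/19.5)/4 = 0.0591. Weighting by numbers therefore costs no precision here.
- **Visit 7 v Visit 4.** One record per subject: Visit 7 for Group 3, Visit 4 for Groups 1 and 2.
- **Unchanged.** The Visit 1 ratio stays unadjusted. Keep the raw GMTs and the exact seroconversion CIs.
- **Beside each adjusted ratio,** report the unadjusted ratio with a Welch CI, which covers unequal variances.

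The cost is SAP wording and a standard regression on data already collected. The downsides are about 10 degrees of freedom, slightly wider CIs if neither covariate is prognostic, a poorer linear fit where many titers are set to 1, and adjusted ratios that will not exactly equal the ratio of the tabulated GMTs.

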### 9.2 Sample Size Calculation

In addition to the below sample size calculations for the immunogenicity endpoints, a sample size of 30 per group also allows for the detection of AEs with an incidence of at least 1 in 10 with a probability of detection of 95% or more.

A sample size of 30 in each group will have 80% power to detect a difference in means of  $0.74 \times$  standard deviation (SD) using a two-group t-test with a 5% two-sided significance level. This means that a difference  $\Delta$  can be detected with  $\Delta / SD > 0.74$ . Taking into account the relative SD of 0.85 for the log10 PRNT titers the detection of a log10 PRNT difference of 0.629 can be detected (or a four-fold increase in titers on the original titer scale). For the ELISA where the log10 SD is at most 0.42 a difference of 0.31 can be detected, i.e. a two-fold increase in titers can be detected.

### 9.3 Trial Cohorts/Datasets to be Evaluated

Analysis of immunogenicity variables will be done on a valid case basis, i.e. for missing observations no imputation technique such as "Last observation carried forward" (LOCF) will be applied, since this could introduce an optimistic bias into the analysis.

#### Full Analysis Set (FAS):

This is the subset of subjects who received at least one vaccination and for whom any data are available.

The main analysis of safety will be performed on this analysis set.

#### Per Protocol Set (PPS):

This is the subset of subjects in the FAS who have received all vaccinations, completed all visits of the active trial phase (Visit 1 to Visit 5 and additionally Visit 6 to Visit 8 for Group 3) and

adhered to all protocol conditions. Subjects with only minor (not relevant) protocol deviations are included into this dataset.

The decision whether a protocol deviation is major or not for the classification of subjects into the various subsets will be made on a case-by-case basis in a data review meeting prior to database lock.

The main analysis of the immunogenicity endpoints will be performed on the PPS. The same statistical procedures will also be applied to the FAS.

